3.3. Randomization and Stratification

Patients will be assigned to one of the two treatment groups with a randomization sequence prepared and maintained centrally by the Data Coordinating Center (DCC). Allocation to the treatment groups will be 1:1. Randomly ordered permuted blocks will be used, with block sizes known only by the DCC. The web-based data management system will provide the treatment assignment for each participant as she is randomized. Thus, the allocation sequence will be concealed from clinical site staff.

Randomization will be stratified by clinical site. It is important that UUI “severity” is comparable in both groups as it is a potential risk factor for treatment failure. Therefore, randomization will also be stratified based on UUI “severity” which will be defined by the number of urgency urinary incontinence episodes (IEs) on diary. This will ensure that women who have more frequent, or more “severe” UUI are equally distributed between the two groups. SUI severity is less of an issue because all subjects will be receiving the same treatment for SUI.

[figure not shown]
Burgio et al,⁴³ identified risk factors for unsuccessful behavioral treatment of urge/urge-predominant MUI. Women who had ≥ 10 IE/week on a 7-day diary at baseline were much less likely to be completely continent after behavioral treatment. Therefore, for a 3-day diary, this would translate into ~ 4 IEs on a 3-day diary as a potential risk factor for treatment failure.

There is limited data to support stratification based on presence of preoperative DO on UDE. One study found that up to 38% will have resolution of DO after MUS.⁴⁴ Other studies suggest that baseline DO is a risk factor for postoperative UUI.⁴⁵ Still other studies even suggest that baseline DO is associated with greater improvement in OAB symptoms postoperatively. Choe et al evaluated 132 women with MUI who underwent MUS and found a higher proportion of women with preoperative DO had complete resolution of OAB symptoms postoperatively compared to those without DO (37% vs. 18%).⁴⁶ A secondary analysis of TOMUS data supported that more severe UUI (by MESA score) was a risk factor for non-SUI sling failure after MUS (or failure due to UUI);²⁹ however, baseline DO was not a risk factor (28% vs 21% objective failure for women with and without DO, respectively).³⁰

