i. Primary outcome: MUI symptoms = UDI-total score

The MID for the UDI-total score published by Dyer et al is estimated to be 35 points.⁵⁰ Assuming a two-sided alpha of .05, SD of 50.4, and true difference in mean change from baseline in UDI-total scores at 1 year between treatment groups of 35, 75 women per group would provide 90% power to detect a statistically significant difference between groups.

ii. Secondary outcome: OAB symptoms= UDI-irritative subscale: For the UDI-irritative subscale, the published MID estimate is 15 points.⁵⁰ Assuming a two-sided alpha of 0.05, SD of 25.6, and true difference in mean change from baseline in UDI-irritative scores at 1 year between treatment groups of 15, 92 women per group would provide 90% power.

iii. Secondary outcome: SUI symptoms = UDI-stress subscale: For the UDI-stress subscale, the published MID is 8 points.⁵¹ Assuming a two-sided alpha of 0.05, SD of 21.5, and true difference in mean change from baseline in UDI-stress scores at 1 year between treatment groups of 8, 200 women per group would provide 90% power to detect a statistically significant difference between groups.

Using 200 per group as our base estimate and adjusting for 15% dropout post-operatively results in a total sample size of 472 randomized to treatment.

Additionally, this sample size will provide approximately 90% power to detect a difference as small as 19 between treatment groups for the UDI-total score, and a difference as small as 16.5 points with 80% power.

6.1.2. Potential limitations of the UDI and primary outcome:

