Amaro 2005 ¹¹⁸	SUI	N=101 Comparative cohort G1 = SUI	Max amp: G1=26.1 (1.15) G2=38.4 (1.33)		P<.001 for all 3 baseline	

		G2=controls	Mean amp: G1=15.4 (.62) G2=28.1 (1.22) Duration (s) G1=8.9 (.17) G2=11.8 (.96)		comparisons	
Gilling 2009 ¹¹⁹	SUI	N=70 RCT G1=Estim G2=Sham	Max amp: G1=17.3 (1.8) G2=15.5 (1.9)	8 wks: G1=19.2 (2) G2=15.1 (1.9)	ND	Subgroup findings: "Patients with poor initial PFM ctx by perinometer randomized to Estim had better UI outcomes than sham" but cannot tease out their PFM scores
Hung 2011 ¹²⁰	Any UI	N=23 PMT Prospective cohort, pre- post- PFM program 65% SUI 35% MUI 39% UUI	Max amp: 27 (15.0)	4 mos: 41 (24.9)	<.001	
Gamerio ¹²¹	SUI vs UUI	N=51 Cross-sectional G1=SUI (N=22) G2=UUI (N=29)	Max amp: G1=26.5 (3) G2=21.7 (.79) Mean peak G1=16.56 (1.19) G2=13.72 (0.56) Duration: G1=9.54 (0.18) G2=8.43 (.42)		P<.001 for all 3 baseline comparisons	Unclear clinical meaning

h. To determine the cost effectiveness of combined midurethral sling (MUS) and peri-operative behavioral/pelvic floor therapy (BPTx) compared to MUS alone on successful treatment of MUI symptoms

Differential mean costs and differential mean QALYs between the two treatment groups will be estimated using multiple regression analysis. Specifically, a generalized linear model with appropriate link function (e.g., log-link) and response probability distribution (e.g., gamma distribution) will be used to analyze costs due to the potential skewness and heteroscedasticity of medical expenditure data, while an ordinary least squares regression will be used for analyzing QALY data. The models will account for treatment group, study site and stratification factors, as well as other characteristics of the subjects that are found to differ significantly between the groups. When estimating QALYs, we will also adjust for subjects' baseline utility scores to account for potential imbalance in baseline utility between the two treatment groups.¹²²

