We will calculate the incremental cost-effectiveness ratio (ICER), which is the differential mean costs divided by the differential mean QALYs between the two groups, to assess the additional costs associated with each additional QALY gained. Our base case analysis will be conducted based on subjects with complete data. Sensitivity analysis will be conducted to include subjects with incomplete data using the multiple imputation method. Non-parametric bootstrapping resampling technique will be used to derive the 95% confidence interval for the ICER.^{118, 123} In addition, cost-effectiveness acceptability curve (CEAC) will be generated to illustrate the likelihood that one treatment is more cost-effective than the other with various ceiling cost-effectiveness ratios.

In the case that a statistically significant difference in changes in utilities (as measured by EQ-5D) between the treatment groups is not detected, we plan to conduct supplemental analyses using alternative

outcome measures, such as incremental cost per treatment success, incremental cost per HRQOL, or incremental cost per satisfaction.

The cost-effectiveness evaluations will be conducted as within-trial comparisons. A decision analytic model will also be developed from trial data to evaluate the trajectory of the cost-effectiveness ratio over a lifetime; assuming an average life expectancy, given the average age of participants at the time of the intervention.

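### The planned bootstrap 95% interval for the ICER has no rule for replicates with a zero or negative QALY difference, so it cannot be interpreted in the non-significant case that the plan foresees

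*Protocol*

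**What the plan says.** Protocol 6.2.3, item h, defines the ICER as a ratio, "which is the differential mean costs divided by the differential mean QALYs between the two groups". It then gives the method for its uncertainty: "Non-parametric bootstrapping resampling technique will be used to derive the 95% confidence interval for the ICER". The type of bootstrap interval is not named, and nothing is said about replicates whose QALY difference is zero or negative.

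The next sentence plans a second summary: a "cost-effectiveness acceptability curve (CEAC) will be generated to illustrate the likelihood that one treatment is more cost-effective than the other" over a range of ceiling ratios. The following paragraph opens "In the case that a statistically significant difference in changes in utilities (as measured by EQ-5D) between the treatment groups is not detected" and responds with supplemental analyses on other outcomes, "such as incremental cost per treatment success, incremental cost per HRQOL, or incremental cost per satisfaction". The ICER interval is not withdrawn or replaced in that case.

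The SAP lists cost-effectiveness as exploratory aim 8 (section 3.1.3) but gives no method for it. Section 9.5 ends with pelvic floor muscle strength. The Protocol text is therefore the only specification.

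**The concern.** A ratio of two differences is easy to interpret only while the denominator keeps one sign. Once replicates fall on both sides of zero, three things go wrong.

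- A negative ratio can come from a cheaper and better result or from a dearer and worse one. On one axis the two cannot be told apart.
- As the QALY difference passes through zero, the ratio jumps between plus and minus infinity. Replicates that are neighbours on the cost-effectiveness plane land at opposite ends of the ordering.
- A positive ratio from a replicate that is cheaper and worse means the reverse of one that is dearer and better.

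An interval read off that ordering has limits that are not a range of cost per QALY. What is at stake is the reading of the economic result. A negative lower limit looks like possible cost saving even when the replicates behind it show the combined treatment costing more and doing worse. The supplemental cost-per-outcome ratios have the same form and can fail in the same way.

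**Working it through.** **Figures in the documents.** No ICER, cost difference, QALY difference or interval is stated, so none can be reproduced. The sample size can: 200/(1 − 0.15) = 235.3, rounded up to 236 per arm, and 2 × 236 = 472. This matches "Using 200 per group as our base estimate and adjusting for 15% dropout post-operatively results in a total sample size of 472 randomized to treatment".

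**Inputs**
- Evaluable women: 200 per arm (Protocol 6.1.1), with "Allocation to the treatment groups will be 1:1" (Protocol 3.3). The base case uses complete data; 200 per arm is assumed for it.
- EQ-5D SD in women with MUI: 0.26 (Protocol Table 6). It is cross-sectional and serves as a proxy for the one-year QALY SD.
- Baseline adjustment: "we will also adjust for subjects' baseline utility scores" (Protocol 6.2.3 item h). The correlation r is not given; 0, 0.5 and 0.7 are assumed.
- QALY gains: assumed, 0 to 0.10.
- Costs: none are given. A mean difference of $600 and an SD of $3,000 are assumed, for illustration only.

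**Step 1. Standard error of the QALY difference.** Residual SD = 0.26 × √(1 − r²), and SE = SD × √(2/200).
- r = 0: SD 0.26, SE 0.026
- r = 0.5: SD 0.225, SE 0.0225
- r = 0.7: SD 0.186, SE 0.0186

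**Step 2. Share of replicates with a negative QALY difference.** At an observed gain d the share is Φ(−d/SE).

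| Observed gain | SE 0.026 | SE 0.0225 | SE 0.0186 |
|---|---|---|---|
| 0 | 50% | 50% | 50% |
| 0.01 | 35% | 33% | 30% |
| 0.02 | 22% | 19% | 14% |
| 0.05 | 2.7% | 1.3% | 0.4% |
| 0.10 | <0.1% | <0.1% | <0.1% |

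These shares belong to an observed gain. For a true gain, averaged over trials, the share is Φ(−d/(SE√2)). With SE 0.026 this is 39%, 29% and 9% at 0.01, 0.02 and 0.05.

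**Step 3. How likely is the foreseen case?** P(non-significant) = Φ(1.96 − d/SE) − Φ(−1.96 − d/SE). At true gains of 0.02, 0.05 and 0.10 it is 88%, 51% and 3% with SE 0.026, and 81%, 23% and <0.1% with SE 0.0186. An observed gain is non-significant below 1.96 × 0.026 = 0.051 or 1.96 × 0.0186 = 0.036.

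**Step 4. What would be printed.** A percentile bootstrap with 5,000 resamples, the assumed costs and SD 0.26 gave:

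| Observed gain | ICER | ICER interval | Net benefit interval at an assumed $50,000/QALY |
|---|---|---|---|
| 0.02 | $30,000 | about −$275,000 to $280,000 | −$2,331 to $3,094 |
| 0.05 | $12,000 | about −$25,000 to $95,000 | −$831 to $4,594 |
| 0.10 | $6,000 | about $0 to $17,700 | $1,669 to $7,094 |

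In the first row about 22% of replicates are dominated. The dominant share follows from the cost SE: 3,000 × √(2/200) = $300, so P(cost difference < 0) = Φ(−600/300) = 2.3%. With costs and QALYs independent, 2.3% × 78% = 1.8%. Negative ratios therefore come mostly from dearer-and-worse replicates, although a negative ICER limit suggests saving. At an observed gain of exactly zero the ICER is undefined, but the net benefit interval is still finite, −$3,331 to $2,094.

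**Step 5. Coverage.** In 4,000 simulated trials per setting (same costs, SD 0.26 and 0.186), the percentile interval covered the true ICER 93% to 98% of the time at true gains of 0.01 to 0.05, and 95% to 96% at 0.10. In a further simulation it fell to 81% to 92% at a true gain of 0.005. Fieller's method held about 95%, but with SD 0.26 its set was not a finite interval in 88% of trials at a gain of 0.02, and in 3% at 0.10.

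**The case against.** The strongest reply has four parts.

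- **The acceptability curve is already planned.** At each ceiling ratio it gives the share of replicates with positive net benefit, so it carries the joint uncertainty in every quadrant. That is correct, and it limits the damage. It does not repair the ICER interval, which the plan reports as well.
- **The Protocol does not name the percentile method.** A careful analyst might handle the quadrants properly. That stands: the gap is a missing rule, not a declared wrong method. But any interval placed on the ratio axis meets the same ambiguity unless a rule is written.
- **Coverage is close to nominal.** A reader might infer that an unstable ratio means the interval misses its 95%. The simulations do not support that, except very near a zero gain. Nor would the interval pass for precise evidence: where the denominator straddles zero it is visibly very wide.
- **The plan names non-significance, not harm.** A reader might infer that the sponsor expects a zero or negative QALY difference. The text does not say so. Its trigger is also defined on changes in utility, whereas the denominator is QALYs. Both come from the EQ-5D, so a non-significant utility result points to a QALY interval that includes zero, but the two tests are not identical.

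Two broader readings also fail. The ICER interval is not uninterpretable in general, because it behaves well at a gain of 0.10. And no faulty interval stands in the documents, because none is stated.

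**Conclusion.** The point holds as a minor one. The plan commits to an interval for a ratio, foresees the situation in which that interval loses its meaning, and responds by adding further ratios. On the Protocol's own EQ-5D SD, the situation is more likely than not for true gains up to about 0.05 QALY without baseline adjustment. With a baseline correlation of 0.7 the probability at 0.05 falls to 23%, but at 0.02 it is still 81%.

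The size rests on a cross-sectional SD standing in for the QALY SD (a time-averaged QALY may vary less), on 200 complete cases per arm, and on assumed gains and correlations. The dollar figures rest on assumed costs and serve only as illustration. The qualitative point needs none of these: it follows from a denominator whose interval includes zero. Cost-effectiveness is an exploratory aim, and no primary or secondary conclusion depends on it.

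**What to change.** Add a short rule to Protocol 6.2.3 item h, or to the SAP, before costs and QALYs are compared by arm:

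1. From the same bootstrap replicates, report incremental net monetary benefit with a 95% interval at willingness-to-pay values named in advance, beside the planned acceptability curve.
2. Show the cost-effectiveness plane with the share of replicates in each quadrant.
3. Report an ICER interval only if a pre-stated share of replicates, for example at least 97.5%, have a QALY difference of the same sign. At that value the rule is the same as requiring the two-sided 95% percentile interval for the QALY difference to exclude zero. Otherwise give the point estimates of the cost and QALY differences with their own intervals.
4. Apply the same sign rule to each supplemental cost-per-outcome ratio, using its own denominator.

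The cost is a few sentences and no new data or resampling. Willingness-to-pay values must be chosen in advance, and the report may carry no ICER interval.

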6.3. Interim data monitoring

Safety outcomes will be assessed at each DSMB meeting. This will include the need for sling revision due to worsening OAB symptoms. Rates of sling revision and other safety outcomes will be compared between treatment groups using Fisher's exact tests and provided to the DSMB. There is no established guidance regarding what sling revision rate is "appropriate" for worsening OAB symptoms in this population: this is one of the exploratory aims of this study.

Since we expect to enroll ESTEEM within 2 years, and since the primary outcome is attained at 12 months following surgery, we propose that no interim analyses of outcomes will be performed. Thus, reports to the DSMB will not include outcome data until primary outcomes have been attained for all participants. At each meeting, the DSMB will be presented with information about enrollment and outcome data attainment (for example, the percent of expected clinic visits that have been completed) to allow them to determine that the study is making reasonable progress.

7. Ethical Concerns/Safety

7.1. Ethical Concerns

As discussed in the background section, current clinical practice varies with respect to treatment of MUI and likely reflects training and experiential bias. Although treatment with behavioral modifications and Kegel exercises have been described as effective first line treatments for mild stress, urge, and mixed urinary incontinence, many patients go on to request further therapy for their condition. For moderate symptoms of SUI or UUI additional therapeutic options are generally offered based on treatment paradigms geared toward each of these conditions. When patients have MUI, clinicians must decide which component (the SUI or the UUI) should be addressed first. There is very little evidence to support a defined treatment strategy in this patient population and most recommendations are based on expert opinion. The only way to test the superiority of one approach over another is in the setting of a randomized clinical trial. We have carefully designed this trial to balance the risks and benefits to subjects. All patients in this study have elected to undergo surgery for SUI. Therefore, they will have already been offered more conservative therapies. We will be assured that women will have either previously tried behavioral or pelvic floor therapy or at least have been offered this treatment because it is an inclusion criteria. In addition all patients will be treated with a midurethral sling and half the patients will be randomized to perioperative supervised BPTx. The potential benefits of the BPTx intervention are improvement of MUI symptoms while the risks are very small. The benefits of BPTx in SUI and UUI alone and MUI have been documented as has the benefit of MUS for patients with SUI. Several studies have also documented an improvement in OAB and MUI symptoms following sling. The added benefit of a combined approach of sling plus BPTx in patients with MUI has not been defined and is the subject of this RCT. Any subject can request additional treatment after 3 months postoperative.

7.2. Informed Consent

Subjects will be clinically examined as part of screening and to ensure eligibility for the study. Those subjects who are candidates for and agree to undergo sling surgery and behavioral treatment for MUI will

be approached for enrollment into the trial. Clinical and research staff will describe the study in detail and answer any questions the subject may have. Written informed consent for trial participation will be obtained at that time. A common template for the research informed consent form will be used by all of the clinical sites, modifying the content or format as necessary to meet the requirements of their respective institutional human subjects committees. This protocol must be approved by the IRBs at the clinical sites and DCC before study implementation.

7.3. Data Safety Monitoring Board

The National Institutes of Health has set up a Data Safety Monitoring Board (DSMB) to oversee all PFDN studies, including this study. Members of the DSMB are independent of the study investigators and represent Urology, Urogynecology and Biostatistics, as well as having a lay member. The DSMB meets every 3 months, or more frequently if requested by the Chair, either in person or by teleconference. This protocol has been approved by the DSMB prior to implementation. Safety outcomes will be assessed in a descriptive manner at each DSMB meeting without formal statistical tests. This will include the need for sling revision due to worsening OAB symptoms. There is no established stopping rule to guide what sling revision rate is “appropriate” for worsening OAB symptoms in this population.

7.4. Reporting of serious adverse events

Each clinical investigator is responsible for reporting serious adverse events (SAEs) to the IRB per their IRB guidelines at their institution, and to the DCC. The DCC Safety Specialist reviews and summarizes the SAE per DCC SAE reporting procedures for the PFDN.

7.5. Adverse events

Adverse events are defined as untoward medical events that are temporally-related to participation in a clinical study, regardless of whether they are causally-related to the study. Adverse events will be collected during the course of this study and reported to the DSMB as described above.

Sling surgery is a commonly performed operation for the treatment of SUI and MUI. Like all surgical interventions it has the risk of bleeding, infection, and injury to surrounding structures. In addition, the sling procedure utilizes polypropylene mesh which can introduce additional risk of mesh complication. These include vaginal mesh extrusion, mesh infection, and bladder or urethral mesh erosion. Complications specific to sling placement include bladder perforation, retropubic hematoma, obturator nerve or vessel injury, groin pain, worsening incontinence, and worsening OAB. The FDA has recently issued guidelines on the use of surgical mesh and has recommended it only be used by trained surgeons. All surgeons participating in this study will be specifically trained to use surgical mesh.

8. Feasibility

The proposed study population has already chosen to undergo surgical treatment and the BPTx intervention is low risk. We have taken care to have comparable arms in a clinical efficacy trial design with inclusion criteria that are not overly-strict; therefore, we do not anticipate particular difficulty in recruitment of MUI patients as encountered in MIMOSA.³⁷ If needed in the postoperative period, medical therapy will not be withheld after 3 months postoperative. Women reporting bothersome OAB symptoms for which they desire additional treatment will be presented their options (additional BPTx and/or FDA approved OAB pharmacologic therapy, or other procedures or surgeries), and additional treatment will be offered. Request for additional treatment for either OAB or SUI postoperatively will be driven by patient preference and clinician judgment in both groups.

9. References

1. Katsumi HK, Rutman MP. Can we predict if overactive bladder symptoms will resolve after sling surgery in women with mixed urinary incontinence? *Curr Urol Rep*;11:328-37.
